A large-scale, prospective cohort study on the association between treatment management models and the prognosis of intrauterine adhesions.

Sponsor: Xiangya Third Hospital, Central South University

Team Leader: Xiangya Third Hospital, Central South University

Funding source: Self-raised funds

Research Institution: Xiangya Third Hospital, Central South
University

Research Leader: [name]

Version number: 2.0

Version Date: August 29, 2024

List of research institution numbers

Name of research institution	serial number
Xiangya Third Hospital of Central South University	01
Changsha Jiangwan Maternity Hospital	02
Changsha Maternal and Child Health Hospital	03

Table of contents

Research Proposal Summary	4
Research Text	6
1. Research Background	6
2. Research Objectives	11
3. Research Design	11
4. Research Content	13
5. Key Evaluation Indicators	18
6. Safety considerations	19
7. Statistical Analysis	19
8. Data integrity and quality assurance	20
9. Ethical Statement	20
10. References	20

Research Proposal Summary

Trial Title: A Large-Scale, Prospective Cohort Study on the Association Between Treatment Management Models and Prognostic Factors of Intrauterine Adhesions

Research Objective: This project aims to explore the efficacy of the new IUA treatment model through a multi-center real-world study and demonstrate its high-quality medical service model, laying the foundation for its future promotion.

Experimental Design: Based on previous research, our team proposed a "new model for the whole-course management and treatment of IUA": preoperative four-dimensional color ultrasound diagnosis and assessment, intraoperative "immediate diagnosis and treatment" cold knife plowing- style adhesion separation using an integrated hysteroscope, postoperative application of a patented intrauterine stent to prevent re-adhesion, postoperative adjuvant therapy with renowned doctors and prescriptions to promote endometrial repair, postoperative four-dimensional color ultrasound assessment and follow-up to replace multiple hysteroscopy examinations, and combined with intraoperative hysteroscopic AI counting of endometrial gland openings and gland density, multimodal data fusion to predict and assess pregnancy prognosis after IUA treatment.

Experimental Procedure: Prospective, Observational Real- Event Study

Selection criteria:

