1.1 Preoperative diagnosis of intrauterine adhesions

There is currently a consensus on the diagnosis and assessment of intrauterine adhesions. The gold standard is hysteroscopy ^[4]. The existing IUA severity scoring standards are all based on hysteroscopic findings. Commonly used scoring standards include the American Fertility Society (AFS) (1988) score ^[5]. The European Society of Gynecological Endoscopy (ESGE) (1998) score ^[6], the March (1978) score ^[7] and the Chinese expert consensus on the clinical diagnosis and treatment of intrauterine adhesions published in 2015 ^[8]. However, hysteroscopy is an invasive examination that depends on the surgeon's skill and subjective impression ^[6]. When the cervical canal, the lower segment of the uterine cavity, or even the uterine cavity is completely closed, hysteroscopy may fail, and the condition of the uterine cavity cannot be fully assessed. It may even cause uterine perforation. In IUA patients with reproductive tract malformations such as unicornuate uterus, it is difficult to determine the correct shape of the uterine cavity under hysteroscopy. Hysteroscopic distension fluid may cause water intoxication. Furthermore, the above limitations, such as the need for anesthesia and high cost, limit its use as a routine screening for intrauterine adhesions. Currently, a large number of studies have demonstrated that four-dimensional ultrasound has a high accuracy in diagnosing intrauterine adhesions. Correlation analysis with hysteroscopy results shows that four-dimensional ultrasound diagnosis of intrauterine adhesions is consistent with hysteroscopy results ^[6]. Studies have also confirmed that multiple ultrasound parameters can accurately screen for intrauterine adhesions ^[7]. Menstrual status, number of intrauterine procedures, uterine cavity morphology, endometrial continuity, endometrial homogeneity, endometrial-myolipin boundary, endometrial blood flow, peristaltic waves, etc. can all be used as evaluation criteria for diagnosing intrauterine adhesions ^[7-8].

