1.2 Surgical treatment of intrauterine adhesions

Since the advent of hysteroscopy, the surgical approach for IUA has gradually

shifted from traditional open surgery, blind curettage, and cervical dilation to... TCRA has become the preferred treatment for IUA . At present, there is still controversy in the clinical practice regarding whether to use energy devices in TCRA. Scholars who support the application of energy devices in TCRA believe that its advantages are simple operation, short operation time, and obvious effects on tissue cutting and hemostasis of bleeding points during operation. However, when energy devices cut the surgical area, the heat released by them can damage the surrounding normal endometrial tissue ^[24] . Non-energy devices mainly use various types of micro forceps and micro scissors to separate and loosen the adhesions in the uterine cavity through blunt and sharp separation, so as to restore the shape of the uterine cavity. This method does not release heat and there is no possibility of thermal damage to the remaining endometrium in the uterine cavity. In order to try to improve the efficacy of traditional cold knife method for TCRA, cold knife plowing- style intrauterine adhesion separation was proposed and gradually began to be used in clinical practice ^[23] . The cold-blade plowing technique , similar to plowing a field, longitudinally severs adhesions and scar tissue within the uterine cavity, exposing the underlying myometrium and any remaining endometrial tissue. Under postoperative medication stimulation, the endometrium has room to grow, and the blood supply from the myometrium can extend upwards to the endometrial layer, improving endometrial blood flow. This is consistent with the approach used by Sun Kun et al. ^[32] This aligns with the view that endometrial volume is related to blood flow parameters. Furthermore, the longitudinal plowing method reduces surgical trauma, which may decrease the likelihood of bleeding and TURP syndrome. Relieving uterine contractions after scar plowing can increase uterine cavity volume, creating more space for endometrial growth .

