after contact, leading to recurrence of adhesions. Therefore, some barriers are needed after surgery to separate the wounds and prevent recurrence of adhesions 错误!未找到引用源。, 错误!未找到引用源。. Over the years, scholars have conducted studies on intrauterine anti-adhesion barriers for intrauterine adhesions, either individually or in different combinations. The most commonly used are intrauterine devices (IUDs), hyaluronic acid gel, Foley catheters, intrauterine balloons, and amniotic membrane transplantation 错误!未找到引用源。, 错误!未找到引用源。. Although efforts have been made to prevent recurrence after surgery, most current research results show that the adjuvant treatment after intrauterine adhesion separation is not effective. In view of this, a new medical silicone rubber material was processed into a uterine cavity-shaped stent, which is specifically used for the postoperative adjuvant treatment of intrauterine adhesions. After nearly 10 years of effort, we have successfully designed and developed a new type of silicone device (called an intrauterine stent) that can theoretically prevent the recurrence of intrauterine adhesions through the physical barrier effect, and applied for patent protection 错误!未找到引用源。. It is made of medical silicone rubber, which is non-irritating to human tissues, has no toxic side effects, is non-carcinogenic, has good biocompatibility, is corrosion resistant, will not swell, soften, or deteriorate due to water absorption, is easy to process and manufacture, is convenient to use, and has good thermal stability. The uterine support mainly consists of a reinforcing ring, a membrane, a tail-shaped structure, and a placement device. The placement device comprises a placement cannula, a positioning block, and a push rod. It is made of medical-grade silicone rubber. The reinforcing ring is elastic, and its shape and size conform to the periphery of the uterine wall. Three drainage grooves are located at the lower end of the reinforcing ring, which facilitates the drainage of intrauterine fluid and reduces the chance of intrauterine infection due to poor drainage. The membrane completely separates the anterior and posterior walls of the uterine cavity, physically preventing adhesions between them. Furthermore, because the membrane is very thin, it exerts almost no pressure on the endometrium it contacts. The tail-shaped structure is primarily responsible for preventing adhesion recurrence. This longitudinal, solid structure connects to the midpoint of the lower segment of the ring and communicates

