However, the characteristics of post-IUA three-dimensional ultrasound images are highly variable and easily affected by machine noise and physician diagnostic experience; how to accurately extract image features is a bottleneck in its application. The information from the four diagnostic methods of TCM is complex, and how to simplify complex information is a challenge for its use in prediction. The integration and enhancement of multidimensional TCM and Western medicine risk factors is a key challenge in establishing a post- IUA infertility risk prediction model. Machine learning technology holds promise for solving these bottlenecks.

2. Research Objectives

2.1 To reveal the intrinsic relationship between three-dimensional ultrasound image characteristics and diagnosis and prognosis in the IUA population;

2.2 Multicenter clinical studies have confirmed the clinical efficacy of the cold knife plowing technique and uterine stent in preventing adhesions;

2.3 Standardize treatment plans for renowned doctors and prescriptions to promote endometrial growth and maintain pregnancy and assist in conception, and confirm their clinical efficacy;

2.4 Construct and validate a multidimensional infertility risk factor prediction model based on integrated traditional Chinese and Western medicine after IUA, and visualize it for easy application;

3. Research Design

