3.3 Evaluate the clinical efficacy of the new integrated traditional Chinese and Western medicine treatment model for IUA through real-world research.

This project conducts prospective and retrospective studies by systematically collecting real-world data and utilizing practical clinical trials. Based on a large database of integrated traditional Chinese and Western medicine treatments for IUA (Intrauterine Adhesion) patients, it compares the clinical efficacy of the new treatment

model with the traditional model. The "New Model for IUA Whole-Process Management and Treatment" includes: preoperative 4D ultrasound diagnosis and assessment; intraoperative "immediate diagnosis and treatment " cold-knife plowing-style adhesion separation using an integrated hysteroscope; postoperative application of a patented uterine stent to prevent re-adhesion; postoperative adjuvant therapy with renowned doctors and prescriptions to promote endometrial repair; postoperative follow-up using 4D ultrasound assessment instead of multiple hysteroscopy examinations; and combining intraoperative hysteroscopic AI counting of endometrial gland openings and gland density, multimodal data fusion to predict and assess pregnancy prognosis after IUA treatment.

3.4 Constructing a Predictive Model for Post-IUA Infertility Risk Based on Machine Learning Integration and Enhancement of Multidimensional Risk Factors from Traditional Chinese and Western Medicine

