Under the leadership of Professors [name] and [name] , a consensus among experts in both traditional Chinese medicine and Western medicine with extensive experience in the diagnosis and treatment of IUA (Intrauterine Adnexation) was jointly developed , outlining the "Expert Consensus on the Integrated Traditional Chinese and Western Medicine Treatment of IUA." This consensus standardizes IUA diagnostic methods and criteria, surgical procedures , traditional Chinese medicine treatment plans, and pregnancy guidance protocols , and is being promoted through clinical training demonstration bases and academic conferences . Relying on the platform of the Traditional Chinese Medicine Clinical Research Base and the National Regional Medical Center for Obstetrics and Gynecology , a big data platform for integrated traditional Chinese and Western medicine diagnosis and treatment has been established. This platform collects IUA diagnosis and treatment data (including imaging data) from IUA-specific alliance units, with Xiangya Third Hospital of Central South University as the chair unit . The data is then recorded and stored in a standardized and structured manner , serving as modeling indicators for the integrated traditional Chinese and Western medicine diagnosis and treatment decision- making system for IUA . By collecting image data from examinations, textual data from Western medicine surgeries and TCM treatment cases, and numerical data from laboratory tests in IUA's integrated traditional Chinese and Western medicine treatments through a big data platform , we first retrospectively collected treatment data from each alliance unit from 2017 to 2022, performed structured storage and cleaning, and completed follow-up to establish a training dataset. Then, we continuously completed high-quality prospective data collection, established the IUA Integrated Traditional Chinese and Western Medicine Treatment Center's official WeChat account, and enabled patient follow-up, real-time storage, export and analysis , real-time efficacy assessment and fertility measurement and evaluation, and established a test dataset for the decision-making model. We continuously expand the sample size to collect treatment data more comprehensively.

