This study employed both internal and external validation methods for model evaluation. Internal validation used a validation set derived from the same source as the training set to assess model reproducibility. This study used a random split validation approach, randomly dividing the dataset into training and validation sets in a 7:3 ratio. The training set data was used to build the model, and the validation set data was used to evaluate model performance. External validation used a prospective dataset collected based on the IUA data platform. The predictive performance of both the Logistic Regression and XGBoost models for predicting post-IUA infertility risk was compared

and evaluated in terms of discriminability and calibration. The Area Under the Receiver Operating Characteristic (AUC) was used for evaluation; a higher AUC value indicates higher discriminability. The DeLong 's test was used to compare the AUC values of the two models to determine statistical significance. The Brier score was used to plot the calibration curve, and the Hosmer- Lemeshow goodness-of-fit test was used to assess model calibration and plot the calibration curve. Finally, to promote the application of predictive models, the Logistic regression model for predicting infertility risk after IUA is visualized using a nomogram, and the Youden index is calculated using the ROC curve method. The optimal cutoff value for the total score of the nomogram is then derived based on the Youden index. The XGBoost model for predicting infertility risk after IUA is presented in an app/webpage format. Two different predictive models are provided for selection in both traditional Chinese medicine and Western medicine clinical practice.

6. Safety considerations

Surgical risks, anesthesia risks, etc.

7. Statistical Analysis Plan (SAP)

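### Section 6 defines no safety outcome, and no section sets uniform, timed harm collection for the comparison of the new and traditional treatment models

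*Protocol*

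**What the plan says.** The whole of section 6 of the Protocol is "Surgical risks, anesthesia risks, etc".

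The comparison is described elsewhere. Section 3.3 says of the project that "it compares the clinical efficacy of the new treatment" model with that of the traditional one, and section 4.2 repeats this. The new model combines cold-knife adhesiolysis, a patented intrauterine stent and a herbal formula taken before and after surgery. Objective 2.2 concerns "the clinical efficacy of the cold knife plowing technique and uterine stent in preventing adhesions", and objective 2.3 concerns the efficacy of the prescriptions. The summary gives the purpose as "laying the foundation for its future promotion".

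The design label is not consistent. The summary calls the study prospective and observational, and the title calls it a cohort study. Section 4.2 places the comparison under interventional research.

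On data, section 4.1 collects "textual data from Western medicine surgeries and TCM treatment cases". It also lists symptoms, diagnoses, laboratory results and treatments. Section 4.3 adds surgical details. Follow-up results are defined in section 4.3 as pregnancy outcomes. The contacts in section 4.1 take place every 3 months and are described as reproductive follow-ups.

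**The concern.** A comparison meant to support wider use of an operation, an implanted device and a medicine has to weigh harm against benefit. Here the benefit side has stated objectives, while the harm side has one line that lists kinds of risk.

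The Protocol itself raises the relevant harms. Of hysteroscopy, section 1.1 says "It may even cause uterine perforation". Section 1.2 suggests that the plowing technique "may decrease the likelihood of bleeding and TURP syndrome". Section 1.3 says of the stent's drainage grooves that their design "reduces the chance of intrauterine infection due to poor drainage". These are statements about safety, and the study defines no outcome that would test them.

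At stake is whether the study can say if infection, barrier problems or drug and herbal reactions are more or less frequent under the new model than under the one it is meant to replace. A later analysis plan cannot restore events that were not recorded, or that were recorded differently in the two groups.

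**Working it through.** The Protocol gives no safety figure to reproduce, so the check is a reading of each place where a harm outcome could stand.

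**1. Is a harm an outcome anywhere?**
- Objectives 2.1 to 2.4: imaging, efficacy of technique and stent, efficacy of the prescriptions, prediction model. Harm objectives: 0 of 4.
- Section 5: discrimination, calibration and cut-off of the prediction models. No clinical harm.
- Section 6: the single line quoted above.
- Section 7: image enhancement, automated grading and infertility prediction. No safety analysis.

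**2. Could routine data supply each event, and equally in both groups?**

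| Event | Possible source | Timed field, same in both groups? |
|---|---|---|
| Perforation, bleeding, fluid overload | Operative text (4.1), surgical details (4.3) | Not stated, but may be recoverable |
| Anesthesia events | Perhaps the operative text | Not stated |
| Later intrauterine infection | Symptoms, diagnoses, laboratory results (4.1) | No postoperative window given |
| Stent or other barrier problems | Perhaps the same items | Not stated |
| Drug or herbal reactions | Perhaps the same items, and the TCM case text (4.1) | Not stated; TCM text exists only for women given TCM |

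The list of symptoms, diagnoses and laboratory results in section 4.1 follows a description of retrospective screening. It sets no period after surgery.

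**3. When are women contacted?**
- The herbal formula is taken before and after surgery (4.2), and the stent is placed at surgery.
- Contacts are 3-monthly, but their starting point is not stated. The two-year follow-up runs from the start of trying to conceive in section 4.1 and from surgery in section 4.3.
- A one-month ultrasound appears in section 4.1, but as something most women in the retrospective data had. It is not a visit fixed for the prospective cohort.

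The Protocol therefore does not settle whether any contact falls in the period of stent and formula use.

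**4. Why unequal capture matters.** Let p be the true event rate and c the probability that an event is recorded, with N for the new and T for the traditional model. The observed rate ratio is then

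(p_N × c_N) / (p_T × c_T) = (p_N / p_T) × (c_N / c_T).

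If the models do not differ in harm, the observed ratio equals c_N / c_T. The Protocol gives no ground for taking that ratio as 1. The new model involves more departments and a TCM record, and the traditional model is not defined. The direction of the error is unknown: closer management could raise recording under the new model, and silence in unstructured notes could lower it.

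**The case against.** The best defense has four parts.

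- **Data are collected.** Section 4.1 lists symptoms, diagnoses and laboratory results, and operative text is stored. Sections 3.2 and 4.1 also speak of monitoring and follow-up examinations, and section 3.3 makes postoperative ultrasound part of the new model. This stands in part. It rules out saying that harms have no field at all. It does not supply a dedicated, timed field that works alike in both groups. Postoperative ultrasound as a component of one model does not provide equal ascertainment.
- **The study is observational.** The summary says so, and an observational study may owe less safety apparatus than a trial. Section 4.2 says otherwise of the comparison, and the Protocol does not resolve the two. Under either label, two models are compared in order to support one of them.
- **Details belong in the SAP or the case report form, neither of which is shown.** This is right for intervals, adjustment and field layout. Which harms are outcomes, in whom and over what period they are collected is a protocol matter, because it must be settled before data collection.
- **The stent period may well be covered.** No stent duration is given, so a reader might infer that the stent weeks fall before the first contact. The Protocol does not show this. It only leaves the matter open.

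**Conclusion.** The point holds as a gap in prespecification and uniform ascertainment. Section 6 defines no safety outcome, and no other section fixes timed harm collection that is the same in both groups. Some events, mainly intraoperative ones, may be recoverable from routine records. Relative harm for later infection, barrier problems and drug or herbal reactions could not be compared reliably.

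A reader might infer that the comparison can report benefit only, or that no harm is recorded. The documents do not support either reading, because operative text, symptoms, diagnoses and laboratory results are collected.

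The size is qualitative: 0 of 4 objectives and none of the measures in sections 5 and 7 concern a harm of treatment. Without a stated complication rate or split by model, any power or precision figure would rest on invented inputs. Efficacy and prediction results are not affected. The change should be made, but the gap does not invalidate the study. The conclusion rests on the Protocol alone; a case report form with uniform harm fields would narrow the point.

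**What to change.** In section 6, name as safety outcomes:
- uterine perforation, bleeding, and fluid overload or TURP syndrome;
- anesthesia events;
- postoperative intrauterine infection;
- problems with the stent or any other barrier;
- adverse reactions to any drug or herbal medicine.

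Record them in the prospective cohort only, because new fields cannot be filled prospectively for retrospective women. Use identical fields in both groups, whatever barrier or medicine was used. Start at the first pre-operative study treatment, or at surgery if there is none, and end at the first 3-monthly contact. State that this contact is counted from surgery. Take the data from the operative record and the existing contacts, with no added visit.

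Record which barrier and medicines each woman received, since the traditional model is not defined. Report event rates by treatment model with 95% confidence intervals, and report later events separately. The analysis detail can sit in the SAP.

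The cost is protocol wording, a few extra fields and a few questions at existing contacts. The limits should be stated: rates may be lower bounds, and rare events may be too few for adjustment.
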